## 8. Eligibility criteria

## **Inclusion criteria**

- Adults ≥ 18 years old
- Able to read and understand English
- Able to give informed consent
- Presenting to primary care with GI symptoms that fulfil the Rome IV criteria for the diagnosis of mixed constipation/ diarrhoea IBS or diarrhoea predominant IBS (diarrhoea is defined as type 6 or 7 stools on the Bristol Stool Chart) for the first time in 5 years
- Taking no prescribed treatment for their symptoms

## **Exclusion criteria**

- Patients not meeting the inclusion criteria
- Unexplained weight loss, rectal bleeding, fever, anaemia, palpable mass or sudden unexplained onset of symptoms
- Previous referral for chronic GI symptoms to a gastroenterologist or GI surgeon
- Previous cholecystectomy
- Previous gastrointestinal surgery of any type except appendicectomy, abdominal wall or femoral hernia repair or diagnostic laparoscopy without surgical intervention
- Past history of Inflammatory Bowel Disease, Coeliac disease, chronic liver or pancreatic disease
- Past history of cancer (except basal cell carcinoma)
- Consultation with any health professional in the last 5 years for abnormal GI symptoms.
- Previous investigations in secondary care for IBS-like symptoms
- Pregnancy at time of start of the study

#### 9. Randomisation

Once eligible patients have signed the structured consent form, they will be randomised 1:1 to either usual following NICE guidance by the GP or a checklist of structured investigations

and management. The Hull Health Trials Unit (HHTU) will provide and maintain a purpose built, web-based data capture system with integrated randomisation. Following assessment of baseline outcomes, participants will be randomised 1:1, IBSSSS score (mild + moderate v severe) and patient gender (male v female). It is not possible to blind nurses or participants to the intervention but researchers analyzing data will be blind to treatment allocation. Access to the randomisation system is managed by HHTU staff and users are granted role-based access restricted to sites they are working at.

## 10. Study processes

## **Nurse training**

Once the study nurses are recruited, they will undergo at least 6 weeks training which will be facilitated by the clinical members of the study team who will also offer ongoing regular support during the trial assisted by two senior nurses working in the community. The nurses will undergo a formal assessment of their competencies to manage the patients recruited for the study before the study opens.

## Recruitment

Social media or posters placed in community pharmacies, GP surgery waiting rooms and other NHS healthcare settings may be used to alert the patients that this trial is ongoing However, to take part in the study, patients need to be referred to the study team by their primary health care team. Patients who present to the primary care team, seem to meet the eligibility criteria, and are interested in participation will be offered a patient information sheet about this study. After giving verbal consent that their details can be passed on to the research team, an email will be sent to the research team with the patients contact number and NHS number using NHS.net email addresses.

The research team will contact the patient at least 24 hours after they have been given the information sheet but within 5 working days and if they meet the eligibility criteria, have read the patient information sheet and wish to take part in the study, they will be invited to attend an appointment with one of the research team at their GP practice or by virtual consultation (as recommended by the Department of Health, whenever possible due to Covid-19 and will be asked to provide written consent which may be e-consent.

Following written consent, all patients will be asked to complete the following questionnaires

- Baseline economic questionnaire
- GSRS symptom score
- HAD (Hospital Anxiety and Depression Score)
- IBS Severity Score (IBSSS) questionnaire
- PHQ-12 SS score
- EQ5D3L
- SF12

## Data of the patient's demographics will be recorded in all patients and include:

- Patient date of birth
- Gender
- Ethnicity
- Occupation
- Alcohol intake as recorded on the summary care record (if available)
- Body Mass Index

- Presence of other comorbidities
- Family history of Coeliac Disease / Inflammatory Bowel Disease (Crohn's /Ulcerative Colitis)/ Bowel cancer and if present which degree relative and at approximately what age was this diagnosed.

In addition, the participants in the trial will be given a questionnaire to complete in which they can enumerate their monthly financial outgoings resulting from their IBS-symptoms and/or consultations/ investigations. Patients will be able to complete these forms on line, over the telephone or on paper each month of the study and the patient will be asked which will be easier for them and if so, how would they like to complete these questionnaires. They will also be asked if they would like to receive a monthly reminder letter/ text/ email/ phone call each month of the study with the next questionnaire. Even if patients have been discharged from clinical follow up, they will be contacted two monthly for 1 year from the date of randomisation to record any health related costs secondary to their IBS symptoms.

The IBSSSS score (mild + moderate v severe) and patient gender (male v female) will be used to stratify the patients via the online randomization system provided by the HHTU.

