## 1. Summary:

**Background:** Irritable Bowel Syndrome (IBS), a chronic relapsing disorder, is diagnosed by symptom-based criteria in the absence of detectable organic causes. IBS frequently leads to severely impaired health related quality of life. IBS-like symptoms, affecting up to 20% of the population, carry significant costs for sufferers, society and healthcare.

The National Institute for Health and Care Excellence (NICE) directs that a limited number of tests are performed when someone presents with IBS-like symptoms. If these tests are normal, lifestyle modifications or specified medication should be prescribed. However, >50% of patients diagnosed with IBS do not improve with this approach.

This may be because alternative conditions are missed particularly when people have IBS-like symptoms characterised by diarrhoea. Evidence suggests that >75% of these patients have other diagnoses, particularly pancreatic insufficiency, microscopic colitis, small bowel intestinal overgrowth carbohydrate malabsorption or bile acid diarrhoea.

Clinical history taking is inaccurate at identifying the cause for symptoms, whereas targeted investigations diagnose these conditions precisely.

In patients with IBS-like symptoms characterised by diarrhoea, no studies have examined the cost-effectiveness and health benefits of early, more comprehensive investigations.

Data show that nurses using checklists, can assess patients accurately, arrange appropriate investigations and apply treatments effectively achieving improvement in symptoms comparable to gastroenterologists even when patients have complex underlying gastrointestinal disorders.

**Methodology:** This study will assess whether patients with IBS-like symptoms fulfilling Rome IV criteria for diagnosis of mixed constipation/diarrhoea or diarrhoea predominant IBS, presenting to primary care benefit from nurse-delivered care, which includes investigations and management denied by NICE, compared with standard care delivered by a GP following NICE recommendations.

Additionally, an economic analysis will be undertaken examining the costs for patients and healthcare in each arm of the study and a qualitative process evaluation, including semi-structured interviews with the nurses, GPs and a selection of patients, to understand the contextual factors which will facilitate wider application of our approach.

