## 5. Hypothesis

In a common, often debilitating condition which is expensive for patients and healthcare, where no single treatment helps even a majority of patients, there are no reported studies which systematically look to see how many of the patients with IBS-like symptoms which include diarrhoea have one of the many possible organic conditions which produce the same symptoms.

This study will use checklists of investigations and apply treatments systematically, to explore whether patients with IBS-like symptoms characterised by predominant diarrhoea presenting in primary care, benefit from a rigorous management approach using well defined, mostly non-invasive and relatively cheap investigations to make a clear diagnosis of organic conditions which otherwise would be missed if the GP follows NICE recommendations.

The underlying hypothesis is that many patients confidently diagnosed using the ROME IV criteria as having diarrhoea predominant or mixed diarrhoea/constipation IBS in fact have treatable organic diagnoses which are currently missed due to inadequate investigation of GI symptoms.

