## Randomised to nurse-led management

Patients will be assessed in the GP surgery or during virtual consultations as detailed above using a 5 step approach. If abnormalities are found at each stage they will be treated and the nurse will only move to the next step if after that treatment the patient has on-going symptoms. For each test listed below, treatment algorithms developed during the nurse training period will be provided detailing management of all possible abnormal results. Standard information sheets will be provided to patients for any condition diagnosed. If a test or treatment is not performed correctly it will be at the discretion of the Chief Investigator whether the test is to be repeated.

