## Data handling and storage

The number of patient appointments and all investigations booked for patients participating in both arms of the study will be recorded using established electronic systems and patient notes.

Drug costs will be assigned using the NHS Tariff and/or BNF prices. Other costs will be calculated using NHS tariffs for 2020-2021.

A random sample of electronic records taken from patients randomised to both arms of this study will be assessed independently to check compliance with treatment protocols.

A trial specific data management plan agreed by the Chief Investigator, Sponsor, HHTU and statistician will be drafted to provide detailed instructions and guidance relevant to database set up, data entry, validation, review, query generation and resolution, quality control processes involving data access and transfer of data to the sponsor at the end of the study and archiving.

All the information obtained about participants in the course of the study is confidential and will be held in accordance with the General Data Protection Regulation (GDPR 2018). Data will be entered into RedCap Cloud, a web-based electronic data capture system. The HHTU Information Systems team will work with the Chief Investigator to design the specification, build and validate the database, which will meet the required regulatory standards. Data are stored on dedicated RCC hardware in EU data centres (including real-time backup) managed by Amazon Web Services to industry standards outlined in ISO 27001, PCI DSS, SOC 1 - 3, FISMA, CIS, CSA, NIST and UK Cloud Security Principles. Data is encrypted at rest and in transit.

Personal data will be collected and processed only for the purpose of allowing the research team to communicate with patients regarding the project. Personal information will not be shared with anybody outside the study. The participants will be allocated a unique ID number. Any hardcopies of data will be maintained in a locked cabinet, separate from the participant database.

A selection of data will be checked against source documents at various timepoints throughout the study in adherence to HHTU's data monitoring plan. All essential documents including source documents will be retained for a minimum period of 5 years after study completion.

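### The patient-cost questions ask about IBS symptoms, a label the nurse arm is meant to replace, so some patient-paid costs may be missed more often in that arm

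*Protocol*

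**What the plan says.** Section 10 of the protocol, in the part on demographics and baseline data, describes two patient-reported cost streams.

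- **Monthly questionnaire.** It lists "monthly financial outgoings resulting from their IBS-symptoms and/or consultations/ investigations". On frequency: "Patients will be able to complete these forms on line, over the telephone or on paper each month of the study".
- **Two-monthly contact.** "Even if patients have been discharged from clinical follow up, they will be contacted two monthly for 1 year from the date of randomisation", and the purpose is "to record any health related costs secondary to their IBS symptoms".

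Healthcare use is collected separately, as the data-handling part of section 10 sets out: "The number of patient appointments and all investigations booked for patients participating in both arms of the study will be recorded using established electronic systems". Clinical notes are the second source named. No link to IBS is required there.

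Section 7 lists an economic evaluation of healthcare and patient costs as a secondary endpoint. Section 6, objective (b), sets cost-effectiveness from the health service's point of view.

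On what the nurse arm is meant to do, section 5 supposes that many patients with an IBS diagnosis "in fact have treatable organic diagnoses which are currently missed due to inadequate investigation of GI symptoms". The Summary puts the background figure high: "Evidence suggests that >75% of these patients have other diagnoses". For the nurse arm, section 10 adds: "Standard information sheets will be provided to patients for any condition diagnosed". Section 9 states that participants cannot be blinded.

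**The concern.** The two-monthly contact asks patients to decide whether a cost follows from their IBS symptoms. That decision depends partly on what they believe is wrong with them, and the intervention is built to change that belief. A nurse-arm patient told that the cause is, say, bile acid diarrhoea or carbohydrate malabsorption may stop counting purchases for it as IBS costs. A GP-arm patient with the same untested condition has no reason to do so. The measurement rule can therefore act differently by arm because of the treatment itself.

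The contact is also worded more narrowly than the monthly questionnaire in the same paragraph, so one patient could properly report an item in one stream and not in the other.

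At stake is the patient-cost part of the secondary endpoint. A later economic analysis plan can choose how to analyse these data, but it cannot recover spending that was never asked about.

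**Working it through.** **No plan figure to reproduce.** The protocol gives no cost data and no expected cost difference. The check is a reading of the cost-collection text, followed by an illustration on assumed inputs.

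**Step 1: which costs depend on the label.**

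| Cost item | Where it would be captured | Depends on the IBS label? |
|---|---|---|
| Appointments, investigations | Electronic systems and notes, both arms (Data handling and storage) | No |
| Travel and other outgoings for consultations or tests | Monthly questionnaire, second limb | No |
| Over-the-counter products, special foods, other patient-paid treatment | Monthly questionnaire, first limb; two-monthly contact | Yes |

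Only the last row is exposed. It matters in this trial because the nurse pathway treats each abnormality found and has a low-FODMAP diet as its third line, so patients may buy such items.

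**Step 2: whether the label differs by arm.** Nurse-arm patients receive tests that can lead to another diagnosis, and written information on it. GP-arm patients are managed under NICE guidance, which section 4 describes as regarding faecal and breath tests as unnecessary. The IBS label is therefore more likely to persist in the GP arm.

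**Step 3: illustration of size.** All inputs are assumed. Let

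- q = share of nurse-arm patients relabelled;
- m = share of their label-dependent costs that they then leave out.

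With equal true costs in the two arms and full reporting in the GP arm, the ratio of recorded to true cost in the nurse arm is 1 − q × m.

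| q | m = 0 | m = 0.25 | m = 0.5 | m = 1 |
|---|---|---|---|---|
| 0.25 | 1.00 | 0.9375 | 0.875 | 0.75 |
| 0.50 | 1.00 | 0.875 | 0.75 | 0.50 |
| 0.75 | 1.00 | 0.8125 | 0.625 | 0.25 |

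For example, q = 0.75 and m = 0.5 gives 1 − 0.75 × 0.5 = 0.625.

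Some relabelling in the GP arm would narrow the gap a little. The Sample size text assumes 5% of controls are treated more like the intervention group. If all of them were relabelled, the nurse-to-GP ratio in that example becomes 0.625 / (1 − 0.05 × 0.5) = 0.625 / 0.975 = 0.641.

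**Limits of the illustration.** It applies only to the third row of the first table. It treats patients as relabelled from the start, whereas diagnosis is stepwise and earlier costs would still carry the IBS label, so it overstates the effect over a full year. The upper q of 0.75 borrows the Summary's background figure, which is not a predicted detection rate for the trial. No document gives m.

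**The case against.** The strongest reply is that the text refers to symptoms, not to a diagnosis. A patient whose diarrhoea turns out to be due to bile acids still has the symptoms that brought them into the trial and can report what they spend on them. The nurse pathway follows those same symptoms from step to step, and every participant completes the IBS severity score at the end. On that reading m is zero. This stands as a possible reading, and it is why no size can be claimed. It does not settle the matter. Elsewhere the protocol often uses the neutral term IBS-like symptoms and separates true IBS from organic disease, while the cost wording drops that neutrality. A patient given another diagnosis could reasonably read the question either way.

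The economic forms are also not reproduced: the Appendices list them by title only, and they may already be worded neutrally. That stands too, so any change to the forms is conditional on what they say. The description in section 10 needs aligning in any case.

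A reader might infer more than the documents support:

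- *That patient costs are collected only when attributed to IBS.* The monthly questionnaire also covers consultations and investigations without that condition.
- *That nurse-arm costs will be under-reported and the cost comparison tilted.* The text supports only that they may be.
- *That the cost-effectiveness result is compromised.* Its stated viewpoint is the health service, and the tests that most distinguish the nurse arm come from records.

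**Conclusion.** The point holds as a wording weakness with a plausible bias that differs by arm and has unknown size. The two-monthly contact is narrower than the monthly questionnaire, and for patient-paid treatment and diet costs both streams rely on patients linking the spending to IBS symptoms. If relabelled patients leave such costs out, the omission falls mainly in the nurse arm and makes it look cheaper on the patient-cost part of the secondary endpoint.

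This rests on three assumptions: that an appreciable share of nurse-arm patients receive another diagnosis, that some of them then stop counting related purchases as IBS costs, and that the forms and contact script follow the wording in section 10. If the second or third fails, the effect is zero. Most of the health-service analysis does not depend on any of them. This is a cheap improvement worth making, not a flaw that undermines the economic evaluation.

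**What to change.** In section 10, describe both the monthly questionnaire and the two-monthly contact with one wording that does not depend on the diagnosis, identical in both arms. For example: *costs because of your bowel or digestive symptoms, or any condition found to be causing them, whatever the diagnosis, and costs of related consultations and investigations*. Check the baseline economic questionnaire, the monthly economic diary and the contact script, and make the same change wherever they carry the present wording.

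The cost is a text change to the protocol and possibly to the forms and the script. Sample size, visits and care are unchanged. A few costs unrelated to the original symptoms may be picked up, but the same question would be put to both arms. If collection has already begun, record the date of the change so that the economic analysis can separate responses before and after it.

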#### Randomisation to the GP arm

If the patient is randomised to the GP arm, the research nurse will make a follow up appointment with the GP surgery. The primary care team managing patients will be given a laminated sheet, summarising NICE recommended management.

## Randomised to nurse-led management

Patients will be assessed in the GP surgery or during virtual consultations as detailed above using a 5 step approach. If abnormalities are found at each stage they will be treated and the nurse will only move to the next step if after that treatment the patient has on-going symptoms. For each test listed below, treatment algorithms developed during the nurse training period will be provided detailing management of all possible abnormal results. Standard information sheets will be provided to patients for any condition diagnosed. If a test or treatment is not performed correctly it will be at the discretion of the Chief Investigator whether the test is to be repeated.

## 1st consultation and initial tests

- Assessment of dietary fibre / caffeine / alcohol intake (using validated questionnaires)
- FBC, U&Es, coeliac screen, CRP, vitamin B12, folate, ESR, TFTs and Vitamin D (if not previously checked in the last 3 months)
- Stool for: 1. Pancreatic Elastase-1; 2. Faecal Calprotectin; 3. FIT 4. Stool for microbiological culture
- Glucose hydrogen methane breath test

## 2nd line test

- A Selenium taurocholic acid (SeHCAT) scan
- Fructose hydrogen methane breath test

## 3rd line

Trial of low FODMAPs diet

## 4th line test

# (These tests are unlikely to be possible during the Covid-19 epidemic, because of restrictions on endoscopy services but will be restarted if circumstances allow )

Upper GI endoscopy with duodenal biopsies and Flexible sigmoidoscopy

## Data handling and storage

The number of patient appointments and all investigations booked for patients participating in both arms of the study will be recorded using established electronic systems and patient notes.

Drug costs will be assigned using the NHS Tariff and/or BNF prices. Other costs will be calculated using NHS tariffs for 2020-2021.

A random sample of electronic records taken from patients randomised to both arms of this study will be assessed independently to check compliance with treatment protocols.

A trial specific data management plan agreed by the Chief Investigator, Sponsor, HHTU and statistician will be drafted to provide detailed instructions and guidance relevant to database set up, data entry, validation, review, query generation and resolution, quality control processes involving data access and transfer of data to the sponsor at the end of the study and archiving.

All the information obtained about participants in the course of the study is confidential and will be held in accordance with the General Data Protection Regulation (GDPR 2018). Data will be entered into RedCap Cloud, a web-based electronic data capture system. The HHTU Information Systems team will work with the Chief Investigator to design the specification, build and validate the database, which will meet the required regulatory standards. Data are stored on dedicated RCC hardware in EU data centres (including real-time backup) managed by Amazon Web Services to industry standards outlined in ISO 27001, PCI DSS, SOC 1 - 3, FISMA, CIS, CSA, NIST and UK Cloud Security Principles. Data is encrypted at rest and in transit.

Personal data will be collected and processed only for the purpose of allowing the research team to communicate with patients regarding the project. Personal information will not be shared with anybody outside the study. The participants will be allocated a unique ID number. Any hardcopies of data will be maintained in a locked cabinet, separate from the participant database.

A selection of data will be checked against source documents at various timepoints throughout the study in adherence to HHTU's data monitoring plan. All essential documents including source documents will be retained for a minimum period of 5 years after study completion.

Only authorised research personnel will have access to the data collected in this study. They may also be looked at by representatives of regulatory authorities and by authorised people from the HHTU to check that the study is being carried out correctly. All will have a duty of confidentiality to research participants and personal identifiable data will not be disclosed outside the research site.

Access to the EDC system is managed by HHTU staff who will create users on behalf of the trial team. Users will be required to complete training and sign a terms of use document. Users are granted role-based access which will be limited only to the sites they are working at.

Anonymised data will be downloaded directly from RCC by authorised research staff for the purposes of reporting and statistical analysis. The anonymised data will be stored on secure network drive in a folder that is only accessible to authorised researchers. Researchers responsible for statistical analysis and reporting will not have authorisation to edit data. Only authorised statisticians will have permissions to download data.

The database will be 'locked' to obtain the final dataset after:

- trial completion (last patient, last visit)
- completion of coding and data entry
- all data queries resolved and the database updated, any serious adverse event queries have been resolved and the database updated
- trial team notified of date of lock

A copy of the final trial dataset and end of trial notification will be sent to the Sponsor before the randomisation list will be released to the study statistician to enable statistical analysis. A copy of individual site's data will be sent to that site.

A copy of the final trial dataset will also be archived by the HHTU and sent to the Chief Investigator. Other authorised researchers requesting access to the dataset for further research may apply through the CI. Applications will be considered in keeping with the publications policy which will be agreed by the Trial Steering Committee.

The HHTU use Box.com for collaborative cloud file storage. The HHTU Box instance is managed by the HHTU with access limited to HHTU staff and authorised members of the research team. Along will all trial documentation Box will be used for storage of interviews by researchers. Box uses EU data centres and complies with (and is independently audited against) the following standards:

- SOC 1, SOC 2 and SOC3
- ISO27001/270018
- Department of Defence Cloud computing Security Requirements Guide
- FedRAMP Level 4
- FISMA
- FINRA/SEC 17a-4
- HIPAA/HITECH

Box acts as a data processor only for the purposes of storage of trial data. Further details on Box data security and GDPR compliance is available here:

https://www.box.com/en-gb/security. The data protection risks of the HHTUs use of Box have been formally evaluated via a data protection impact assessment.

